4.10 Secondary Endpoint Analysis

All secondary endpoint analyses will be descriptive.

4.10.1 Contraceptive Efficacy

The Pearl Index and 95% CI will be calculated for Years 4 and 5, as well as cumulatively through Years 4 and 5. The calculation will follow the same rules used for the primary analysis for the initial 3 years.

Time to on-treatment pregnancy from the date of successful insertion will be analyzed via Kaplan-Meier method for the EP population. Cumulative probability of on-treatment pregnancy (contraceptive failure rate) at the end of Years 1 through 5 will be estimated. The complementary log-log transformation will be used to construct 95% CIs. The estimated pregnancy probability and confidence bound via Kaplan-Meier method multiplied by 100 is expected to be comparable to the Pearl Index point estimate and confidence bound via Poisson distribution to provide supportive evidence of contraceptive efficacy.

As with the primary endpoint analysis, cycles during which no intercourse occurs or backup methods of contraception (including emergency contraception) are used will be excluded from the analysis unless the subject had an on-treatment pregnancy in that cycle. The remaining cycles will be compressed to provide contiguous cycles for the time-to-event analysis. This analysis will use the time-to-event and censor variables (CYCLENAC and PREGNANCY) defined in the exposure section.

A sensitivity analysis will be performed without excluding those cycles with backup contraception or no intercourse. The sensitivity analysis will use the time-to-event and censor variables (CYCLEN and PREGNANCY) defined in the exposure section.

Life-table analysis via Kaplan-Meier method will be repeated for the following subgroups:

- Race (white, non-white)
- BMI group at enrollment
- Age group at enrollment
- Parity at enrollment

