1.1.3 Phase 2, Open-label, Single-Arm Study

A US Phase 2, multicenter, open-label, single-arm study (Protocol CMDOC-0008) was conducted to evaluate the effectiveness, study device placement, safety and tolerability of VeraCept at 12 months, with a 24-month extension phase to a total of 36-months study participation. The final 36-month analysis has been completed. A total of 286 subjects, parous and nulliparous premenopausal women between the ages of 18-40 years, were enrolled at 12 investigational sites in the US. VeraCept was successfully inserted in 283 subjects (99%). Placement was reported to be "easy" or "very easy" for 259/283 subjects (92%) in the safety population. At least some device placement pain was reported by 240/283 subjects (85%). Device placement pain was rated as "some pain" by 137/283 subjects (48%), "painful" by 49/283 subjects (17%), "moderately painful" by 42/283 subjects (15%), and "very painful" by 12/283 subjects (4%). Most subjects (86%) did not require mechanical dilation.

The one-year findings demonstrated that VeraCept was effective through 13 cycles of use: a single pregnancy was reported among the 250 subjects in the evaluable for pregnancy (EP) population, equating to a Pearl index of 0.52 (95% CI: 0.01, 2.87). By Kaplan-Meier analysis, the cumulative probability for remaining pregnancy free through Day 365 was 0.995.

The favorable safety, tolerability, and effectiveness data observed at one year in the Phase 2

study supported the initiation of the Phase 3 clinical trial for VeraCept.

Subjects were allowed to remain in the study, in the extension phase, for an additional 24 months and for a total of 36 months of study participation. Overall, 177/286 subjects (62%) chose to continue in the extension phase and of those, 107/177 subjects (60%) completed 36 months. The 36-month findings continue to demonstrate VeraCept's contraceptive efficacy. A second pregnancy occurred during the extension phase of the study,

with a cumulative 3-year Pearl index for all EP subjects of 0.73 (95% CI: 0.09, 2.65).

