20.7.1 Contraceptive Efficacy

The Pearl Index will be calculated for Years 4, 5, 6, 7 and 8, as well as cumulatively through Years 4 through 8.

A life table analysis (using Kaplan-Meier) of pregnancies will be performed for the EP population to present the cumulative pregnancy percentage for Years 1 through 8. As with the primary endpoint analysis, cycles with backup contraception or no intercourse will be excluded from the analysis and the remaining cycles will be compressed to provide contiguous cycles. A sensitivity analysis will be performed without excluding those cycles with backup contraception or no intercourse to assess the results without the need to compress cycles.

Separate analyses will be performed only for the last 3 years of the study (Years 6-8) using the EP population. The cumulative Pearl Index for Years 6 to 8 will be calculated as well as the cumulative pregnancy percentage for Years 6 to 8 using a life table analysis (Kaplan-Meier).

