4.1.5 Exposure Periods

The first exposure cycle starts on Day 1 of successful study drug insertion. A full exposure cycle is comprised of 28 days. One woman-year comprises thirteen 28-day cycles. The following exposure periods are defined for analysis in terms of planned study days and study cycles to facilitate the efficacy and certain safety analyses.

Exposure Period	Study Day of Period Start (PSTDY)	Study Day of Period End (PENDY)
Year 1 (Cycle 1- Cycle 13)	1	364
Year 2 (Cycle 14-Cycle 26)	365	728
Year 3 (Cycle 27-Cycle 39)	729	1092
Year 4 (Cycle 40-Cycle 52)	1093	1456
Year 5 (Cycle 53-Cycle 65)	1457	1820
First 2 Years (Cycle 1-Cycle 26)	1	728
First 3 Years (Cycle 1-Cycle 39)	1	1092
First 4 Years (Cycle 1-Cycle 52)	1	1456
5 Years (Cycle 1-Cycle 65)	1	1820

Type of Events and Study Day During an Exposure Period

ЕТҮРЕ	Event	Study Day of Event (EVTDY)		
A	Expulsion	Study Day of Expulsion date		
В	Expulsion followed by conception within 7 days	Study Day of Expulsion date		
С	Removal	Study Day of Removal date		
D	Removal followed by conception within 7 days	Study Day of Removal date		
Е	Pregnancy before expulsion	Study Day of Conception date		
F	Pregnancy before removal	Study Day of Conception date		
Н	Lost to follow-up without pregnancy, expulsion or removal	Study Day of Last Date Device in Situ.		
I	Complete period without pregnancy, expulsion or removal	Study Day of Period End Date		

Note: Removal due to partial expulsion will be treated as expulsion

Exposure Duration in Days (EXDUR):

if EVTDY-PSTDY>0 then EXDUR = min(EVTDY-PSTDY+1, PENDY-PSTDY+1); else EXDUR=.;

Exposure Duration in Cycles (NCYCF) = EXDUR/28

Number of Completed Cycles (NCYCC) = INT(NCYCF)

Number Relevant Cycles (NCYCR)

- =NCYCC+1 if last partial cycle is >=23 days
- =NCYCC+1 if last partial cycle ETYPE is B or D or E or F
- =NCYCC, otherwise.

Number of Cycles with back-up contraceptives (including emergency contraception) or no intercourse within the period or there is no diary data (NCYCEXCL):

Exclude from NCYCEXCL the cycle in which the subject had an on-treatment pregnancy (ETYPE is B, D, E, F).

Back-up contraceptives or intercourse history are recorded in subject's diary.

If there are missing values then they will be handled as follows:

Missing back-up contraceptive diary entries will be treated as no back-up contraceptive use.

Missing intercourse diary will be treated as no intercourse.

Number of Evaluable Cycles (NCYCEV) = NCYCR-NCYCEXCL

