4.2 Analysis Populations

4.2.1 Analysis Populations

• ITT

All subjects who underwent the study drug placement procedure, regardless of whether the study drug was successfully placed or not.

• Safety:

ITT subjects who had the study drug successfully placed

• Safety Subgroup (36-45 years):

Subjects in the Safety population who were between 36 to 45 years of age (inclusive) at enrollment.

• Evaluable for Pregnancy (EP):

ITT subjects who had VeraCept placed successfully and meet requirements 1, 2 and 3 as follows. Subjects must also meet either requirement 4 or requirement 5 to be part of the EP study population:

- 1. Be post-menarcheal up to 35 years of age (inclusive) at enrollment
- 2. Have at least one report of pregnancy status after being enrolled
- 3. Do not have pre-treatment pregnancy, which is defined as the estimated conception date being before the insertion date.

AND

4. Have at least 1 cycle of e-diary with intercourse and without any backup contraception or emergency contraception

OR

5. Have an on-treatment pregnancy, which is defined as the estimated conception date being on or after the insertion date and no more than 7 days after the VeraCept is removed or expelled.

Subjects with major protocol violations that are deemed to have had a material impact on the primary efficacy assessment will be excluded from EP analysis population. Exclusions based on major protocol deviations will be reviewed and approved by the Sebela and its designee.

• Evaluable for Cycle Control (ECYC):

ITT subjects with at least one cycle for which:

1. A pregnancy did not occur;

AND

2. There was an assessment of bleeding reported by the subject.

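### The uncompressed Kaplan-Meier sensitivity analysis stays in the EP set, so women with no qualifying diary cycle add no time at risk unless they conceive

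*SAP*

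**What the plan says.** SAP 4.10.1 sets the population for the pregnancy life table: "Time to on-treatment pregnancy from the date of successful insertion will be analyzed via Kaplan-Meier method for the EP population". Protocol 20.7.1 agrees: "A life table analysis (using Kaplan-Meier) of pregnancies will be performed for the EP population".

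In the main life table, cycles with backup contraception or no intercourse are removed unless an on-treatment pregnancy fell in them, and the remaining cycles are closed up (CYCLENAC). The SAP then adds: "A sensitivity analysis will be performed without excluding those cycles with backup contraception or no intercourse". Its only stated change is the time variable: "The sensitivity analysis will use the time-to-event and censor variables (CYCLEN and PREGNANCY) defined in the exposure section". Protocol 20.7.1 gives the aim as seeing the results when no compression is needed.

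EP membership (SAP 4.2.1, protocol 20.1) needs requirements 1 to 3 plus one of two others. Requirement 4 is "Have at least 1 cycle of e-diary with intercourse and without any backup contraception or emergency contraception". Requirement 5 begins "Have an on-treatment pregnancy, which is defined as the estimated conception date being on or after the insertion date" and extends to 7 days after removal or expulsion. SAP 4.1.5 also places cycles without diary data among the excluded ones and adds: "Missing intercourse diary will be treated as no intercourse".

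**The concern.** Requirement 4 applies the cycle exclusion to the whole woman. If all her cycles had backup contraception, no intercourse or no intercourse diary, and she did not conceive, she is outside EP and contributes no cycles, even in the analysis meant to drop the exclusions. If she did conceive, requirement 5 brings her in with an event. Her entry depends on the outcome being estimated.

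At stake is what the check can show. It should tell the reader how far the pregnancy percentage depends on the diary rules. Part of the excluded time stays out, so the sensitivity result sits closer to the main result than one with no exclusions would.

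**Working it through.** **1. Who changes between the two analyses**

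| Woman (placed, up to 35, requirements 1 to 3 met) | Main analysis (CYCLENAC) | Sensitivity analysis (CYCLEN) |
|---|---|---|
| At least one qualifying diary cycle | Evaluable cycles only | All cycles |
| No qualifying cycle, no pregnancy | Not in EP | Not in EP |
| No qualifying cycle, on-treatment pregnancy | In EP, event | In EP, event, all cycles |

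Row 1 does what the sensitivity sentence promises. Rows 2 and 3 show the gap. Requirements 4 and 5 together lose no pregnancy and remove only pregnancy-free time.

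**2. Size by algebra**

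The plan gives no figure for this effect, so there is none to reproduce. Let x be the pregnancies, T the EP time and T0 the time of the women in row 2.

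- Rate in EP: x/T. Rate with row 2 included: x/(T + T0). Ratio: 1 + T0/T.
- Let f be the share of women with no qualifying cycle and q their mean follow-up relative to the others. Pregnancies are few, so T0/T is about q·f/(1-f).
- With q = 1 the ratio is 1/(1-f). For f = 1%: 1/0.99 = 1.010. For f = 5%: 1/0.95 = 1.053.

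The documents do not give f; 1% and 5% are assumptions. Applied to the 1,480 planned women up to 35, they mean about 15 and 74 women.

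**3. Check by simulation**

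Inputs:
- 620 of 1,480 women reach 3 years (SAP 3.7). Assuming exponential discontinuation, the rate is -ln(620/1,480)/3 = 0.290 per year.
- 0.52 pregnancies per 100 woman-years in both groups. This is the Phase 2 one-year Pearl Index in protocol 1.1.3, used here as an assumption.

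Uncompressed 3-year Kaplan-Meier pregnancy percentage:

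| Assumed f | Discontinuation of women with no qualifying cycle | EP as written | All placed, requirements 1 to 3 | Ratio |
|---|---|---|---|---|
| 1% | same as others | 1.534 | 1.519 | 1.010 |
| 5% | same as others | 1.606 | 1.527 | 1.052 |
| 1% | five times as fast | 1.517 | 1.513 | 1.003 |
| 5% | five times as fast | 1.551 | 1.528 | 1.015 |

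Small differences between rows within a column include simulation noise.

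The algebra agrees. Mean follow-up to 3 years is (1 - 620/1,480)/0.290 = 2.00 years at the common rate. At five times that rate (1.45 per year) it is (1 - e^(-4.35))/1.45 = 0.68 years. So q = 0.34, and for f = 5% the ratio is 1 + 0.34 × 0.05/0.95 = 1.018.

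**4. Against sampling error**

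1,480 × 2.00 gives about 2,965 woman-years. A 3-year risk of 2.0% is a yearly rate of -ln(0.98)/3 = 0.00673, or about 20 pregnancies. The exact Poisson limits of 12.2 to 30.9 correspond to roughly 1.2% to 3.1%. At f = 5% and q = 1, 2.0% would read 2.0 × 1.053 = 2.1%, well inside that interval.

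**The case against.** **The protocol's stated aim is met.** That aim is to avoid compression, and CYCLEN restores every cycle for every woman in EP. This stands. A reader might infer that the sensitivity analysis leaves the exclusions fully in force; the documents do not support that. The gap is confined to women with no qualifying cycle.

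**Changing the population would blur the comparison.** It is said that holding EP fixed isolates compression. This does not stand. A non-pregnant woman with every cycle excluded has essentially no compressed time, so adding her to the main analysis would change almost nothing. Adding her to the uncompressed analysis measures the cycle exclusion itself.

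**The bias is conservative and nothing formal depends on it.** This stands. The percentage is pushed up, against the product, and all secondary analyses are descriptive.

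**Phase 2 offers a figure for f.** A reader might infer an f near 12%: 283 women had a successful placement and "a single pregnancy was reported among the 250 subjects in the evaluable for pregnancy (EP) population", so (283 - 250)/283 = 11.7% were outside EP. The documents do not support using it. That study enrolled women aged 18 to 40, its EP definition is not given, and the 33 may have been out for any reason. The Phase 3 entry criteria also require expected coitus at least monthly and willingness to rely on the device alone, so few women should be followed for long without a qualifying cycle.

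**Other tables already show the exclusions.** Largely true. SAP 4.8 tabulates relevant, evaluable and excluded cycles for Safety and EP, SAP 4.4 gives Safety tables a column for age up to 35, and SAP 4.5 lists reasons for exclusion from each population. A reader might infer that the diary rules otherwise go unexamined; they do not. What is missing is a pregnancy estimate without them.

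**The event count is not strictly complete.** Correct. EP also drops women with major violations that materially affect efficacy, and that could remove pregnancies. The upward-only statement therefore covers requirements 4 and 5 alone.

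**Conclusion.** The point holds in a narrow form: the planned check is complete for cycles within EP and incomplete for women outside it, and entry for those women depends on whether they conceived. Through requirements 4 and 5 the sensitivity percentage can only be too high.

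The bound of about 1/(1-f) assumes that the women left out are followed no longer than the others. The effect is probably small. No sample size or precision statement is affected. It would be wrong to conclude that efficacy is flattered or that the primary analysis is invalid: the bias runs the other way and lies in a descriptive secondary analysis. The case for changing it is that the selection is avoidable at very little cost.

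**What to change.** In SAP 4.10.1 and protocol 20.7.1:

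- Run the sensitivity analysis with CYCLEN and PREGNANCY in all successfully placed women who meet EP requirements 1 to 3, without applying requirements 4 and 5.
- State whether the major-violation exclusion applies. The same handling as in EP keeps the comparison clean.
- Report how many women and cycles this adds to EP, which also shows f.
- Give a companion Pearl Index in the same set with relevant cycles (NCYCR) as the denominator. SAP 4.8 already tabulates these cycles.
- Leave the primary EP analysis unchanged.

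The cost is one population flag, one table and a few lines of text, with no new data. The supplied SAP is written to protocol version 3.0 and five years, while the protocol now runs to eight, so a revision is due in any case. If the 3-year analysis has already been run, label the added result accordingly. The drawback is that the wider set includes some women who were not at risk of pregnancy, so it should be read beside the EP result and not in place of it.

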4.10.2 Study Drug Placement

Study drug placement data will be summarized for the ITT and Safety populations while study drug removal data will be summarized for the Safety population only. The study drug placement and removal data will be presented in the listings.

4.10.2.1 Study Drug Placement

The following parameters will be reported in the table for study drug placement:

Number (%) of subjects who

- Attempted first insertion
 - Had successful first insertion
 - o Failed first insertion
- Attempted second insertion after failed first insertion
 - Had successful second insertion
 - o Failed second insertion

Total number of insertions

Number of failed insertions

- Number (%) of failed insertions by reason of failure
- Number (%) of insertions with local anesthesia
- Number (%) of insertions required cervical dilation
- Insertion ease and pain
 - o Frequency distribution of insertion ease as assessed by investigator
 - Frequency distribution of insertion pain assessed immediately after insertion as reported by subject
 - Frequency distribution of insertion pain assessed immediately after insertion will also be summarized for subjects with prophylactic pain medication prior to insertion as well as for subjects without prophylactic pain medication prior to insertion.

4.10.2.2 Study Drug Removal

The following parameters will be reported in the table for the initial three years' follow-up and at the end of the 5-year study.

Number (%) of subjects who had study drug removal

- Frequency distribution of removal ease as assessed by investigator
- Frequency distribution of removal pain as reported by subject

4.11 Multiplicity Adjustment

There is no planned interim to stop the trial before the end of 3 years to claim contraceptive efficacy. There is no need for multiplicity adjustment for type I error α .

4.12 Safety and Tolerability

Adverse events will be coded and classified by SOC and PT using MedDRA. The summaries of AEs will be limited to TEAEs. Number (%) of subjects reporting AEs and SAEs will be summarized for the Safety population. A few selected AE and SAE tables will also be summarized for the ITT population.

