15.2 Definition of an Adverse Event

An adverse event is any untoward medical occurrence in a clinical investigation subject administered an investigational product and which does not necessarily have to have a causal relationship with this treatment. An AE can, therefore, be any unfavorable and unintended sign (that could include a clinically significant abnormal laboratory finding), symptom, or disease temporally associated with the use of a medicinal product, whether or not considered related to the medicinal product.

Any AE (i.e., a new event or an exacerbation of a pre-existing condition) with an onset from the day of informed consent/assent through VeraCept removal or expulsion should be recorded as an AE on the eCRF. An event that is discovered during the screening visit that clearly started or was acquired prior to obtaining informed consent (e.g., positive cervical infection test, positive cervical pathology) should be recorded as medical history and not as an AE. All AEs must be recorded regardless of the severity or relationship to study drug. It is important that investigators also report all AEs that result in expulsion or removal of the investigational product being studied, whether serious or non-serious.

Pregnancy is an outcome, and not an AE in this study.

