20.7.3 Safety and Tolerability

The following safety and tolerability analyses will be performed:

- Incidence of AEs and SAEs will be summarized for the ITT population as well as for the Safety populations for all subjects and the 36 to 45-year-old safety subpopulation. The number and percentage of subjects with each AE and SAE will be presented in a table by MedDRA system-organ class and preferred term. Summaries will be presented by relationship to VeraCept and/or VeraCept placement or removal procedure and the severity of the adverse event. All AEs will be summarized, including these AESIs:
 - Pain during insertion
 - Pelvic infection (PID or endometritis)
 - Expulsion
 - Uterine perforation
 - Dysmenorrhea
 - Abdominal pain
- Bleeding and spotting patterns will be summarized (per Mishell [12]) for the ECYC population for the first year of treatment by the number of days in each 28-day cycle with bleeding or spotting, bleeding only and spotting only.
- The insertion pain assessed immediately after insertion will be summarized...
- Cumulative VeraCept continuation rates for Years 1 through 8 will be summarized using Kaplan-Meier methods for the Safety population. The number and percentage of subjects with each reason for discontinuation will be summarized.
- Cumulative VeraCept expulsion rates at for Years 1 through 8 will be summarized using Kaplan-Meier methods for the Safety population.

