20.9 Determination of Sample Size

Approximately 1,605 subjects will be enrolled on an open label basis. It is planned that 1,480 of the 1,605 VeraCept subjects will be in the up to 35-year age range and the remaining 125 subjects will be in the 36 to 45-year age range. It is expected that at least 40% of enrolled subjects will be nulliparous.

It is expected that 1,480 post-menarcheal VeraCept subjects up to age 35 years will provide at least 620 women with at least 3 years of use of VeraCept. It is expected that the study will have 577 woman-years of use in Year 3 of the study who are evaluable for the Pearl Index analysis. This will allow for the Pearl Index calculation for Years 1, 2, and 3 of the study and for the cumulative 3 years to have an upper bound of the 95% confidence interval no more than 1 unit above the point estimate of the Pearl Index.

It is also expected that 1,480 post-menarcheal VeraCept subjects up to age 35 years will provide at least 350 women with 5 years of use of VeraCept.

The 1,605 enrolled VeraCept subjects are expected to provide over 17,000 cycles (28-day cycles) of exposure in Year 1. Over 54,000 VeraCept cycles are expected to be collected during the course of the 5-year study.

The 1,605 enrolled VeraCept subjects are expected to provide at least 200 women with 8 years of use of VeraCept. Over 65,000 VeraCept cycles are expected to be collected during the course of the 8-year study. These 8-year projections assume that 10% of the subjects that complete 5-years of use will not consent to extending their use of VeraCept beyond Year 5.

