3.7 Determination of Sample Size

Approximately 1,605 subjects will be enrolled into this study to receive VeraCept on an open-label basis. It is planned that 1,480 of the 1,605 subjects will be in the up to 35-year age range and the remaining 125 subjects will be in the 36- to 45-year age range. It is expected that at least 40% of enrolled subjects will be nulliparous.

It is expected that 1,480 post-menarcheal subjects up to age 35 years will provide at least 620 women with at least 3 years of use of VeraCept. It is expected that the study will have 577 woman-years of use in Year 3 of the study that are evaluable for the Pearl Index analysis. This will allow for the Pearl Index calculation for Years 1, 2, and 3 of the study and for the cumulative 3 years to have an upper bound of the 95% CI no more than 1 unit above the point estimate of the Pearl Index.

It is also expected that 1,480 post-menarcheal VeraCept subjects up to age 35 years will provide at least 350 women with 5 years of use of VeraCept.

The 1,605 enrolled VeraCept subjects are expected to provide over 17,000 cycles (28-day cycles) of exposure in Year 1. Over 54,000 VeraCept cycles are expected to be collected during the course of the 5-year study.

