4.12.2 Adverse Events by System Organ Class and Preferred Term

The incidence of AEs and SAE will be summarized by MedDRA primary SOC and PT. The summary will include the total number and percentage of subjects reporting an AE within an SOC and/or PT.

The incidence of AEs by SOC and PT for the Safety and ITT populations

The incidence of AEs by SOC and PT by maximum severity for the Safety population

The incidence of AEs by SOC and PT by closest relationship to study drug use for the Safety population

The incidence of AEs by SOC and PT by closest relationship to drug placement/removal procedure for the Safety and ITT populations

The incidence of SAEs by SOC and PT for the Safety and ITT populations

The incidence of SAEs by SOC and PT by maximum severity for the Safety population

The incidence of SAEs by SOC and PT by closest relationship to study drug use for the Safety population

The incidence of SAEs by SOC and PT by closest relationship to drug placement/removal procedure for the Safety and ITT populations

The incidence of AE leading to study drug removal by SOC and PT for the Safety population

The incidence of AE leading to study discontinuation by SOC and PT for the Safety population

Listing of AE leading to death for the ITT population

Incidence of AEs experienced by at least 5% of subjects by SOC and PT for the Safety population

Incidence of AESIs(e.g. pain during insertion, pelvic inflammatory disease, ectopic pregnancies, uterine perforations, expulsions, uterine perforation, dysmenorrhea, and abdominal pain) will be summarized for Safety and ITT populations.

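### Apart from expulsion and Year 1 menstrual pain, adverse events are summarised only as crude percentages, which fall below the risk of continued use for events that keep accruing

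*SAP*

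**What the plan says.** SAP 4.12 gives the general rule: "Number (%) of subjects reporting AEs and SAEs will be summarized for the Safety population", with selected tables repeated for the ITT population. SAP 4.12.2 applies it to the coded tables: "The summary will include the total number and percentage of subjects reporting an AE within an SOC and/or PT". The overall summary (SAP 4.12.1) and the subgroup tables (SAP 4.12.5) follow the same pattern. Protocol 20.7.3 agrees: "The number and percentage of subjects with each AE and SAE will be presented in a table by MedDRA system-organ class and preferred term".

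The recording window depends on how long the device stays in. Under protocol 15.2, any AE with onset from consent "through VeraCept removal or expulsion should be recorded as an AE on the eCRF". Protocol 15.12 adds later SAEs that seem reasonably related to the study drug.

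Some outcomes are handled over time:
- Expulsion, which is recorded as an AE (protocol 12.11) and is an AESI, has yearly Kaplan-Meier rates with 95% confidence intervals (SAP 4.1.8 and 4.12.9).
- Continuation is also analysed by Kaplan-Meier (SAP 4.12.8).
- Diary bleeding and menstrual pain or cramping are reported by cycle in Year 1 (SAP 4.12.6 and 4.12.7).
- Ectopic pregnancies are not excluded from the on-treatment pregnancies in the Pearl Index and Kaplan-Meier analyses, but they get no rate of their own.

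SAP 4.8 derives woman-years for the Safety population, but no AE table uses them. AE onset relative to insertion appears only in a listing (SAP 4.12.4).

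**The concern.** The denominator of each AE percentage is every woman with a device placed, whether she kept it four months or eight years. Once the device is out she can add almost nothing to the numerator. When most women are expected to leave before the end of the period, a percentage over that period mixes the frequency of the event with the speed at which women stop using the device.

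Pelvic infection, ectopic pregnancy, uterine perforation, dysmenorrhea and abdominal pain are named secondary safety endpoints. Protocol 5.2 says the data will be assessed for an initial filing for 3 years of use, and the data up to 8 years for filings to extend it. A prescriber will want to know the risk over that period for a woman who keeps the device, and whether it changes with device age. The planned tables answer neither question. The crude figure also decides which events enter the SAP 4.12.2 table of AEs in at least 5% of subjects.

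**Working it through.** **Inputs.** Protocol 20.9: "Approximately 1,605 subjects will be enrolled on an open label basis"; the enrolled women are "expected to provide over 17,000 cycles (28-day cycles) of exposure in Year 1"; and "Over 65,000 VeraCept cycles are expected to be collected during the course of the 8-year study". SAP 3.7: "Over 54,000 VeraCept cycles are expected to be collected during the course of the 5-year study". Both sections project at least 620 of 1,480 women aged up to 35 with 3 years of use and at least 350 of 1,480 with 5 years. Protocol 20.9 adds at least 200 of 1,605 with 8 years, and assumes 10% of 5-year completers decline the extension. SAP 4.1.5: 13 cycles make one woman-year.

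**Retention.** 620/1,480 = 41.9% at 3 years; 350/1,480 = 23.6% at 5 years; 200/1,605 = 12.5% at 8 years.

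**Mean exposure from the stated cycles.**
- 8 years: 65,000/13/1,605 = 3.1 woman-years.
- 5 years: 54,000/13/1,605 = 2.6 woman-years.
- Year 1: 17,000/13/1,605 = 0.81 woman-years.

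**Do the projections fit together?** Draw a piecewise-exponential retention curve S(t) through the three points, with the 10% drop after Year 5. Apply it to all 1,605 women, assuming that the older group leaves at the same pace. Cycles = (area under S) × 1,605 × 13. With a constant loss hazard over Years 0 to 3 this gives 65,434 cycles at 8 years, 55,118 at 5 years and 18,112 in Year 1, in line with the stated figures. Forcing Year 1 to exactly 17,000 cycles (retention of about 65% at 1 year) gives 52,337 at 5 years and 62,653 at 8 years, within 4% of the stated figures. The two curves bracket a plausible range; mean exposure at 3 years is 1.9 to 2.0 years.

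**Crude percentage against risk with continued use.** For a constant event rate r, independent of removal:
- crude over T years = ∫₀ᵀ r·exp(−rt)·S(t) dt
- risk if the device is kept = 1 − exp(−rT)

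The documents give no event rates, so r was varied from 0.1 to 10 per 100 woman-years. One-year retention was set at 66% and 75%, close to the two curves above.

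| Horizon | Crude, r = 1 per 100 | Kept, r = 1 per 100 | Ratio, all r |
|---|---|---|---|
| 3 years | 1.9–2.0% | 3.0% | 1.5–1.6 |
| 5 years | 2.5–2.6% | 4.9% | 1.8–2.0 |
| 8 years | 2.9–3.1% | 7.7% | 2.2–2.7 |

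**Hand check.** A constant 25% yearly loss nearly matches the projections (0.75³ = 42%, 0.75⁵ = 24%). The loss hazard is λ = −ln 0.75 = 0.288, and crude = r/(r+λ) × [1 − exp(−(r+λ)T)]. At r = 0.05:
- T = 3: crude 9.4%, kept 13.9%.
- T = 8: crude 13.8%, kept 33.0%.

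**Effect on the 5% table.** At 2 per 100 woman-years the crude 5-year figure is 4.8 to 5.1% and the risk with continued use is 9.5%. Whether such an event is tabulated would depend on the pace of discontinuation.

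**Front-loaded events.** Take a total cumulative hazard of 0.05 that decays after placement, with 66% retention at 1 year. The ratio is 1.02 if mean onset is 2 to 3 weeks, 1.10 if 3 months, and 1.3 to 1.4 if 1 year.

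**The case against.** The strongest counter-argument is that the crude percentage is a legitimate quantity. On-device follow-up is complete for a woman whose device is out. Apart from women lost to follow-up or otherwise censored with the device in place, the percentage approximates the probability of an on-device event with removal as a competing event. The crude formula above is that quantity. This stands. It means that a cumulative incidence with removal as a competing event would return the same low figure. Only 1 minus Kaplan-Meier, censoring at removal, gives the higher one, and it needs removal to be unrelated to the event. That is doubtful for pain or bleeding, which may themselves prompt removal.

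A reader might infer that every AE is reported only as a crude percentage. The documents do not support that: expulsion is an AE with yearly Kaplan-Meier rates, menstrual pain is shown by cycle in Year 1, and ectopic pregnancies are not excluded from the pregnancy analyses.

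A reader might also infer that all the tables understate risk, or that the SAP plans 8-year crude tables. Insertion pain and procedural events cluster at placement, where the difference is negligible. The SAP is written to protocol version 3.0 and analyses at 3 and 5 years (SAP 4.4); only protocol version 7.0 reaches 8 years.

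Finally, the retention figures are minimum projections, two of them for women aged up to 35 only. Better retention would shrink the ratios.

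**Conclusion.** The point holds in a limited form. For harms that keep accruing and have no time-based analysis of their own (e.g. pelvic infection, ectopic pregnancy as a separate outcome, later pain or bleeding), the planned percentages describe what happened in a cohort that mostly left early. They do not describe the risk of keeping the device for the intended period. If retention matches the plan's minimum projections, the gap is about 1.5 to 1.6 fold at 3 years and 1.8 to 2.0 fold at 5 years, the SAP's own horizons. It is 2.2 to 2.7 fold at 8 years, under the current protocol's horizon only.

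These sizes rest on assumed event rates, a constant hazard, independence of event and removal, and the younger group's retention applied to everyone. They show the direction and order of the gap and do not predict results. The crude counts are not wrong and should stay. This is an inexpensive improvement to a descriptive safety analysis, and it applies to the other device harms what the SAP already does for expulsion.

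**What to change.** Keep the crude counts. In SAP 4.12.2, for pelvic infection, uterine perforation, ectopic pregnancy, dysmenorrhea, abdominal pain, SAEs and device-related AEs, add:

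1. **Incidence of first event per 100 woman-years, overall and by year of use.** The denominator should be Safety-population time on device including partial cycles, censored at first event. It should not be the evaluable cycles, which drop time for reasons specific to pregnancy risk. Related SAEs learned of after removal stay in the counts but outside the on-device rate.
2. **1 minus Kaplan-Meier for first event at the yearly landmarks used for expulsion**, censoring at removal as in SAP 4.12.9. The conception-censoring rule there cannot carry over to ectopic pregnancy, which is itself the event.
3. **A statement under the tables** that the Kaplan-Meier figure assumes removal is independent of the event, and that the crude percentage approximates on-device risk with removal as a competing event.

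The yearly landmarks should run to the horizon of the analysis, which is Year 8 once the SAP is aligned with protocol version 7.0.

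The cost is a few tables and one derivation, time to first event, since SAP 4.8 gives only total exposure. The data are already collected and no study procedure changes. The Kaplan-Meier figures for accruing events will look less favourable than the crude ones.
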